- Duration of the study: The primary study will be approximately 6 months for each enrolled subject, the duration of the study extension will be 18 up to 24 months.
 - Primary Vaccination
 - Epoch 001: Screening
 - Epoch 002: Primary vaccination starting at Visit 1 (Day 1) and ending just before the Visit 3 (Day 31)
 - Epoch 003: Follow-up after Visit 3 (Day 31) to Phone Contact 1 on (Day 181)
 - End of Primary Study: Subjects must sign the ICF addendum to join the study extension.
 - Study Extension: 6-month period starting at the beginning of 12 months up to the beginning of 18th month after Visit 1 (\geq 12 to <18 months)
 - Epoch 004: 2nd dose vaccination starting from Visit 4 (up -7 days prior to vaccination) to Visit 6 (Day 31 post 2nd dose vaccination)
 - Epoch 005: 2nd dose vaccination Study Follow-up 2 starting after Visit 6 (Day 31 post 2nd dose vaccination) and ending at Phone Contact 3 (Day 181 post 2nd vaccination).
- Primary completion Date (PCD): Visit 3 (Day 31) or last visit of Primary Epoch 002

Refer to list of abbreviations for the definition of PCD.

- End of Study (EoS): Last testing results released of samples collected at Visit 6, to occur no later than 8 months after last subject last visit (LSLV), which occurs with phone contact 3 on Day 181 post 2nd vaccination.

Refer to list of abbreviations for the definition of EoS.

- **Study groups:**

Table 2 Study groups, pooled study groups (Amended 03-DEC-2020)

Pooled Groups label in tables	Pooled definition for footnote	Group label in tables	Group definition for footnote
RSV120_dTpa	Subjects who received RSV120 and dTpa	XRSV120_dTpa	Subject who received RSV MAT 120 and Boostrix-ex-US (dTpa_500)
		URSV120_dTpa	Subjects who received RSV MAT 120 and Boostrix-US (dTpa_300)
RSV120_Placebo	Subjects who received RSV120 and placebo	XPlacebo_RSV120	Subject who received RSV MAT 120 and Placebo
		UPlacebo_RSV120	Subject who received RSV MAT 120 and Placebo
RSV60_dTpa	Subjects who received RSV60 and dTpa	XRSV60_dTpa	Subjects who received RSV MAT 60 and Boostrix-ex-US (dTpa_500)
		URSV60_dTpa	Subjects who received RSV MAT 60 and Boostrix-US (dTpa_300)
RSV60_Placebo	Subjects who received RSV60 and placebo	XPlacebo_RSV60	Subjects who received RSV MAT 60 and Placebo
		UPlacebo_RSV60	Subject who received RSV MAT 60 and Placebo
dTpa_Placebo	Subjects who received Boostrix(dTpa) and Placebo	XPlacebo_dTpa	Subject who received Boostrix-ex-US (dTpa_500) and Placebo
		UPlacebo_dTpa	Subject who received Boostrix-US (dTpa_300) and Placebo
RSV_placebo	Subjects who received RSV60 and placebo combined with subjects who received RSV120 and placebo		
RSV_dTpa	Subjects who received RSV60 and dTpa combined with subjects who received RSV 120 and dTpa		

Table 3 Study groups, treatment and epochs foreseen in the study (Amended 03-DEC-2020)

Study Groups	Number of subjects	Age (Min-Max)	Treatment name 1	Treatment name 2	Epochs (Blinding)			Epoch 004 (open Label)	Epoch 005 (open study)
					Epoch 001 (Screening)	Epoch 002 (observer-blind)	Epoch 003 (single-blind)		
XRSV120_dTpa	50	18 – 45 years	RSV MAT 120 Boostrix-ex-US (dTpa_500)	RSV MAT 120	x	x	x	x	x
Xplacebo_RSV120	50	18 – 45 years	RSV MAT 120 Placebo	RSV MAT 120	x	x	x	x	x
XRSV60_dTpa	50	18 – 45 years	RSV MAT 60 Boostrix-ex-US (dTpa_500)	RSV MAT 120	x	x	x	x	x
Xplacebo_RSV60	50	18 – 45 years	RSV MAT 60 Placebo	RSV MAT 120	x	x	x	x	x
Xplacebo_dTpa	50	18 – 45 years	Boostrix-ex-US (dTpa_500) Placebo	RSV MAT 120	x	x	x	x	x
URSV120_dTpa	50	18 – 45 years	RSV MAT 120 Boostrix-US (dTpa_300)	RSV MAT 120	x	x	x	x	x
Uplacebo_RSV120	50	18 – 45 years	RSV MAT 120 Placebo	RSV MAT 120	x	x	x	x	x
URSV60_dTpa	50	18 – 45 years	RSV MAT 60 Boostrix-US	RSV MAT 120	x	x	x	x	x
Uplacebo_RSV60	50	18 – 45 years	RSV MAT 60 Placebo	RSV MAT 120	x	x	x	x	x
Uplacebo_dTpa	50	18 – 45 years	Boostrix-US (dTpa_300) Placebo	RSV MAT 120	x	x	x	x	x

- **Control:** (active comparator).
- **Treatment allocation:** (randomised stratified).
- **Blinding:** As described in [Table 3](#).
- **Data collection:** standardised Electronic Case Report Form (eCRF). Solicited symptoms will be collected using a subject paper Diary (pDiary).
- **Safety monitoring:**

If the investigator becomes aware of a holding rule being met, he/she will suspend vaccination and will inform GSK immediately.

4. ANALYSIS SETS *(Amended 03-DEC-2020)*

4.1. Definition

For purposes of analysis, the following analysis sets are defined:

Analysis Set	Description
Enrolled	Subjects who agreed to participate in a clinical study after completion of the informed consent process. And subject is not a screen failure.
Exposed	All subjects who received at least 1 dose of the study treatment. The allocation in a group is done in function of the administered treatment.
Per Protocol	All subjects who received at least 1 dose of the study treatment to which they are randomised and have post-vaccination data minus subjects with protocol deviations that lead to exclusion
Solicited Safety	All subjects who received at least 1 dose of the study treatment (Exposed Set) who have solicited safety data

4.1.1. Exposed Set

The ES will include all subjects who received at least 1 dose of the study treatment.

- A **safety** analysis based on the ES will include all subjects who received at least 1 dose of the study treatment.

4.1.2. Per Protocol Analysis Set

Per protocol analysis set will be defined by time points. It will include all subjects who received at least 1 dose of the study treatment to which they are randomised and have post-vaccination data minus subjects with protocol deviations that lead to exclusion at Screening, Day 8 and Day 31 post 1st dose, Visit 4 and Visit 6 post 2nd dose.

- An **immunogenicity** analysis based on the ES will include all vaccinated subjects for whom immunogenicity data are available, if, in any study group and at any timepoint, the percentage of enrolled or vaccinated subjects with serological results excluded from the Per Protocol set for analysis of immunogenicity is 5% or more.

4.2. Criteria for eliminating data from Analysis Sets

Elimination codes are used to identify subjects to be eliminated from analysis. Detail is provided below for each set.

4.2.1. Elimination from Exposed Set (ES)

Code 1030 (Study vaccine not administered at all), 800 (Fraudulent data) and code 900 (invalid informed consent or fraudulent data) will be used for identifying subjects eliminated from ES

4.2.2. Elimination from Per-protocol analysis Set (PPS)

Code 1030 (Study vaccine not administered at all), 800 (Fraudulent data) and code 900 (invalid informed consent or fraudulent data) will be used for identifying subjects eliminated from PPS

4.2.2.1. Excluded subjects from Per-protocol analysis set

A subject will be excluded from the PPS analysis under the following conditions

Table 4 Elimination code and condition (Amended 03-DEC-2020)

Code	Condition under which the code is used	Visit (timepoints) where the code is applicable	Applicable for analysis set/endpoint
800	Fraudulent data	All	All
900	Invalid informed consent	All	All
1030	Study vaccine not administered at all	All	Safety, immunogenicity
1040.Vx+*	Administration of concomitant vaccine(s) forbidden in the protocol	All	Immunogenicity
1050	Randomisation failure	All	Immunogenicity
1060	Randomisation code was broken	All	Immunogenicity
1070**	Subjects got vaccinated with the correct vaccine but containing an incorrect volume	All	Immunogenicity
1070**	Vaccination not according to protocol (site of injection, route of administration, wrong replacement of study treatment administered)	All	Immunogenicity
1070**	Study treatment not prepared as per protocol (e.g. reconstitution)	All	Immunogenicity
1070**	Other deviations related to wrong study treatment/administration/dose	All	Immunogenicity
1070**	Study treatment administered while contraindication	All	Immunogenicity
1080	Vaccine temperature deviation	All	Immunogenicity
1090	Expired vaccine administered	All	Immunogenicity
2010	Protocol violation (inclusion/exclusion criteria) DOB – VAC – 18-45 years	All	Immunogenicity

CONFIDENTIAL

209141 (RSV MAT-011)
Statistical Analysis Plan Amendment 4

Code	Condition under which the code is used	Visit (timepoints) where the code is applicable	Applicable for analysis set/endpoint
2150	Failure to report safety events per protocol	All	Safety
2040.Vx+*	Administration of any medication forbidden by the protocol	Visit 2/Day 8 Visit 3/Day 31 Visit 4 Visit 6	Immunogenicity
2040.Vx+*	Device, excluded by the protocol, was administered	Visit 2/Day 8 Visit 3/Day 31 Visit 6	Immunogenicity
2050.Vx+*	Intercurrent medical conditions which are exclusionary as per protocol	Visit 3/Day 31 Visit 4 Visit 6	Immunogenicity
2060.Vx+*	Concomitant infection related to the vaccine which may influence immune response	Visit 2/Day 8 Visit 3/Day 31 Visit 6	Immunogenicity
2070.Vx+*	Concomitant infection not related to the vaccine but may influence immune response	Visit 2/Day 8 Visit 3/Day 31 Visit 4 Visit 6	Immunogenicity
2090.Vx	Subjects did not comply with blood sample schedule: 
 For PPS at Day 8, check the interval from vaccination to day 8 BS = 7 – 10 days; For PPS at Day 31, check the interval from vaccination to day 31 BS = 30 – 45 days; For PPS at Visit 6, check the interval from Visit to Visit 5 BS = 365 – 548 days; 	Visit 2/Day 8 Visit 3/Day 31 Visit 4 Visit 6	Immunogenicity
2100.Vx	Serological results not available post-vaccination	Visit 2/Day 8 Visit 3/Day 31 Visit 4 Visit 6	Immunogenicity
2120.Vx*	Obvious incoherence or abnormality or error in data	Visit 2/Day 8 Visit 3/Day 31 Visit 4 Visit 6	Immunogenicity
2130.Vx	Testing performed on samples not aligned with ICF	Visit 2/Day 8 Visit 3/Day 31 Visit 4 Visit 6	Immunogenicity

*Attribution of these elimination codes to subject need CRDL review of individual listing

** Attribution of code 1070 to a subject requires CRDL confirmation

Vx+ indicates subjects whose immunogenicity data will be eliminated from a specific visit onwards; Vx indicates subjects whose immunogenicity data will be eliminated from a specific visit.

DOB-Date of Birth, VAC-Vaccination, BS- Blood Sample

4.2.3. Elimination from solicited safety set**4.2.3.1. Excluded subjects****4.2.3.1.1. *Solicited safety set***

Code 1030 (Study vaccine not administered at all), code 800 (fraudulent data) and code 900 (invalid informed consent) and code 1160 (no post-vaccination solicited safety data) will be used for identifying subjects eliminated from the solicited safety set.

5. STATISTICAL ANALYSES**5.1. Demography****5.1.1. Analysis of demographics/baseline characteristics planned in the protocol**

These analyses will be performed on the Exposed set and on the Per protocol set for immunogenicity.

For all subjects, demographic characteristics (e.g., age at vaccination (18–32; 33–45 years), race and ethnicity, vaccination history will be summarized by overall and vaccine group using descriptive statistics.

- Frequency tables will be generated for categorical variables such as age
- Mean, standard deviation, median, minimum and maximum will be provided for continuous data such as age, height, weight and body mass index (BMI).

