- The Medical Monitor should be contacted if there are any questions regarding concomitant or prior therapy.

**7.5.2. Concomitant medications/products/vaccines that may lead to the elimination of a subject from per-protocol analyses**

The use of the following concomitant medications/products/vaccines will not require withdrawal of the subject from the study but may determine a subject's evaluability in the per-protocol analysis. See Section 10.2 for populations to be analysed.

**CONFIDENTIAL**209141 (RSV MAT-011)  
Protocol Amendment 6 Final

Any investigational or non-registered product (drug or vaccine) other than the study vaccine(s) used during the study period.

- Immunosuppressants or other immune-modifying drugs administered chronically (i.e. more than 14 days in total) during the study period. For corticosteroids, this will mean prednisone  $\geq 5$  mg/day (for adult subjects) or  $\geq 0.5$  mg/kg/day (for paediatric subjects), or equivalent. Inhaled and topical steroids are allowed.
- Long-acting immune-modifying drugs administered at any time during the study period (e.g. infliximab).
- A vaccine not foreseen by the study protocol administered during the period starting 30 days before the dose and ending 30 days after each dose of vaccine(s).

Note: In case an emergency mass vaccination for an unforeseen public health threat (e.g.: a pandemic) is organised by the public health authorities, outside the routine immunisation program, the time period described above can be reduced if necessary for that vaccine provided it is licensed and used according to its Summary of Product Characteristics (SmPC) or Prescribing Information and according to the local governmental recommendations and provided a written approval of the Sponsor is obtained.

- Immunoglobulins and/or any blood products administered during the study period.
- Drug and/or alcohol abuse.

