## **7.6. Intercurrent medical conditions that may lead to elimination of a subject from per-protocol analyses**

At each study visit subsequent to the vaccination visit, it must be verified if the subject has experienced or is experiencing any intercurrent medical condition that may lead to elimination from per protocol analysis. If it is the case, the condition(s) must be recorded in the eCRF.

For example, subjects may be eliminated from the per-protocol set for immunogenicity if, during the study, they incur a condition that has the capability of altering their immune response (i.e. varicella) or are confirmed to have an alteration of their initial immune status.

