2. OBJECTIVES/ENDPOINTS

Table 1 Study objectives and endpoints (Amended 03-DEC-2020)

[figure not shown]
Objectives	Endpoints
Primary (US + ex-US data to be pooled)	
Safety	Safety

 To evaluate the safety and reactogenicity of 2 dose levels (60 and 120 µg) of RSVPreF3 when given alone or co-administered with dTpa from Vaccination up to Day 31. 	
 Occurrence of any Adverse Events (AEs) from Vaccination to Day 31: 
 Occurrence of each solicited local AEs at the site of injection in both limbs from Vaccination to Day 8; Occurrence of solicited general AEs from Vaccination to Day 8; Occurrence of any unsolicited AEs from Vaccination to Day 31; Occurrence of Serious Adverse Events (SAEs) from Vaccination to Day 31.

 To evaluate the safety of a 2nd dose of RSVPreF3 given from 12 up to 18 months post 1st Dose up to Day 31 days post 2nd dose vaccination 	
 Occurrence of any AEs from 2nd dose to Day 31 post-2nd dose vaccination, for all subjects: Occurrence of each solicited local AE at the site of injection in both deltoids from 2nd dose vaccination to Day 8 post-2nd dose vaccination Occurrence of solicited general AEs from 2nd dose vaccination to Day 8 post 2nd dose vaccination Occurrence of any unsolicited AEs from 2nd dose to Day 31 post- 2nd dose vaccination Occurrence of Serious Adverse Events (SAEs) from 2nd dose vaccination to Day 31 post 2nd dose vaccination.
Immunogenicity	Immunogenicity

 To evaluate the humoral immune response to 2 dose levels (60 and 120 µg) of RSVPreF3 when given alone and co-administered with dTpa, at Screening, Day 8 and Day 31 post 1st dose vaccination 	
 RSV A neutralizing antibody titers at Screening, Day 8 and Day 31 in all groups RSV IgG antibody concentrations at Screening, Day 8 and Day 31.
Secondary (US and ex-US data to be considered pooled, then separately)	
Safety	Safety

 To evaluate the safety and reactogenicity of 2 dose levels (60 and 120 µg) of RSVPreF3 when given 	
 Occurrence of any AEs from Vaccination to Day 31, for all subjects:

Objectives	Endpoints

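### SAP Table 4 omits Visit 2/Day 8 from the intercurrent-condition code 2050.Vx+, so a non-infectious condition recorded by Day 8 leaves the Day 8 sample in the per-protocol set

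*SAP*

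**What the plan says.** SAP 4.1.2 builds the per-protocol set separately for each timepoint, and SAP 4.2.2.1, Table 4, lists the codes that remove data from it. Code 2050.Vx+ covers "Intercurrent medical conditions which are exclusionary as per protocol" and is listed for Visit 3/Day 31, Visit 4 and Visit 6. The footnote explains the suffix: "Vx+ indicates subjects whose immunogenicity data will be eliminated from a specific visit onwards". Codes with a single asterisk, 2050 among them, are not applied mechanically: "Attribution of these elimination codes to subject need CRDL review of individual listing".

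Protocol 7.6 says when such conditions are looked for: "At each study visit subsequent to the vaccination visit, it must be verified if the subject has experienced or is experiencing any intercurrent medical condition". The first mark in the matching row of the schedule of activities is at Visit 2.

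Day 8 is one of the primary immunogenicity timepoints in SAP Table 1: "RSV A neutralizing antibody titers at Screening, Day 8 and Day 31 in all groups".

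For non-study vaccines, code 1040.Vx+ ("Administration of concomitant vaccine(s) forbidden in the protocol") is listed for all visits. Protocol 7.5.2 defines the exposure dose by dose: "A vaccine not foreseen by the study protocol administered during the period starting 30 days before the dose and ending 30 days after each dose".

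**The concern.** The protocol gathers the information at Visit 2 for the purpose of deciding per-protocol membership, yet the SAP provides no way to use it at Visit 2 under the code meant for it. The same woman could then be judged unfit for the per-protocol set at Day 31 because of something already known on Day 8, while her Day 8 titre still counts in the Day 8 per-protocol geometric mean and in the co-administration ratio at that visit. No reason is given. The two older SAP versions bound in the same file have the same gap, which suggests it was inherited rather than chosen.

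A lesser matter is the onward reach of Vx+. The SAP now includes a second dose and a Visit 6 sample, but the suffix has no stop at dose 2. Read literally, an event around dose 1 can remove a sample taken more than a year later.

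**Working it through.** **Step 1. Visit scopes in SAP Table 4, side by side.**

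| Code | Event | Visits listed |
|---|---|---|
| 1040.Vx+ | non-study vaccine | all |
| 2040.Vx+ | forbidden medication | 2, 3, 4, 6 |
| 2040.Vx+ | excluded device | 2, 3, 6 |
| 2050.Vx+ | intercurrent condition | 3, 4, 6 |
| 2060.Vx+ | infection related to the vaccine | 2, 3, 6 |
| 2070.Vx+ | infection not related to the vaccine | 2, 3, 4, 6 |

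Code 2050 is the only Vx+ code in the table that cannot act at Visit 2. The visit column could mean where a code may start or which samples it may remove. Under either reading, 2050 leaves Day 8 in.

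**Step 2. What can still reach Day 8 by another route.** Protocol 7.6 gives two examples. Varicella is an infection, and 2070 ("Concomitant infection not related to the vaccine but may influence immune response") lists Visit 2. A confirmed change in immune status is not an infection, and if it arises after vaccination 2050 is the evident code. The gap is therefore confined to non-infectious conditions recorded by Day 8.

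**Step 3. Size at Day 8.** The documents give no event rate and no effect size, so these are assumptions: k = 1 to 3 affected women in a pooled group of n = 100, each with a titre depressed by a factor f = 3 to 10. The group geometric mean is multiplied by f^(−k/n):

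- k = 1: 3^(−0.01) = 0.989 and 10^(−0.01) = 0.977, a fall of 1.1% or 2.3%.
- k = 3: 3^(−0.03) = 0.968 and 10^(−0.03) = 0.933, a fall of 3.2% or 6.7%.

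If all affected women are in one arm, the ratio between arms moves by the same factor. For scale, protocol Table 19 gives a 90% CI of 0.81 to 1.24 around a ratio of 1.0 at n = 100 and SD 0.4.

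**Step 4. Reach of Vx+ past dose 2.** The inputs are in protocol Table 4: Visit 1 to Visit 5 is 365 to 548 days, and Visit 5 to Visit 6 is 30 to 45 days. Visit 6 is thus 365 + 30 = 395 to 548 + 45 = 593 days after dose 1. With the 90-day special-circumstances limit in protocol Table 10, the upper end is 548 + 90 = 638 days. A forbidden vaccine given near dose 1 can, if the code is attributed, remove a sample that far away, whereas protocol 7.5.2 sets the window around each dose.

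**The case against.** The case for leaving the table alone has real substance:

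- Healthy women aged 18 to 45 will seldom develop a non-infectious immune-altering condition within 7 to 10 days of vaccination, and infections and forbidden medication already act at Visit 2.
- Protocol 7.6 requires checking and recording; it permits elimination but does not require it.
- The Day 8 between-group model is labelled exploratory, SAP section 6 makes comparisons descriptive, and the non-inferiority criterion in SAP 5.2.2.1 is at Day 31, where 2050 does apply.

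All of this stands, and it limits the importance of the point. It does not explain the omission. CRDL review cannot supply a visit that the table does not list. Nor does the complementary Exposed Set analysis help at Day 8, since it contains the same woman.

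A reader might infer that no intercurrent event can remove a Day 8 sample. That is true of code 2050 only.

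A reader might also infer that the SAP wrongly discards valid second-dose responses at Visit 6. The documents do not support that. Nothing in them bars a first-dose event from affecting Visit 6. The objective is the response to dose 2 following a first dose of 60 or 120 µg, and results are summarised by first-dose level, so excluding women with a compromised first response is defensible. Attribution needs case review, and exclusions of 5% or more in any group (3 of 50, or 5 of a pooled 100) trigger the Exposed Set analysis. What remains is that the review has no stated criterion for carry-over, in an extension conducted open label.

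**Conclusion.** The omission of Visit 2/Day 8 from code 2050.Vx+ is a real mismatch between SAP and protocol and should be corrected. It affects membership of one primary-timepoint per-protocol set, for non-infectious conditions only. Under the assumed range the Day 8 geometric mean shifts by 1.1% to 6.7%, small against the planned precision, and the Day 31 non-inferiority assessment does not change. The low cost of the correction, more than the size of the effect, is the reason to make it.

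The reach of Vx+ beyond dose 2 is a matter for clarification, not an error. The text allows removal of Visit 6 at 395 to 593 days after dose 1, subject to CRDL review. For code 1040 this sits awkwardly with the per-dose vaccine window. The SAP should say which behaviour it intends.

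**What to change.** 1. Add Visit 2/Day 8 to the visit list of code 2050.Vx+. This is a change of table wording with no new data. The downside is possibly one or two fewer Day 8 per-protocol samples. If the Day 31 analysis has already been run, record this as a change in SAP section 8.

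2. State in advance, for each Vx+ code, whether an event attached to dose 1 carries past Visit 5. Two cautions apply:
   - Do not borrow the 30-day vaccine window for infections under 2070. The protocol sets that window for vaccines only. Visit 6 may fall 30 to 45 days after dose 2, or up to 90 under special circumstances, so an infection on days 31 to 45 could precede the sample yet fall outside the window.
   - If a rule restores Visit 6 while Visit 4 stays removed, say how the Visit 6 over Visit 4 ratio is handled, because those women would enter the Visit 6 geometric mean but not the per-protocol ratio.

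   The cost is a few lines of SAP text.

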
 
To evaluate the safety of 2nd dose of RSVPreF3 given from 12 to up to 18 months post 1st dose vaccination up to Day 181 post 2nd dose vaccination.
 
	
 
Occurrence of SAEs from 2nd dose vaccination up to Day 181 post-2nd dose vaccination.
 

Immunogenicity	Immunogenicity

 
To evaluate the humoral immune response and persistence to 2 dose levels (60 and 120 µg) of RSVPreF3 when given alone and co-administered with dTpa at Screening, Day 8, and Day 31 post 1st dose vaccination, and at 12 to 18 months by formulation.
 
	
 
RSV A neutralizing antibody titers at Screening, Day 8, Day 31, and a single timepoint between 12 to 18 months post 1st vaccination.
 
RSV IgG antibody concentrations at Screening, Day 8, Day 31, and a single timepoint between 12 to 18 months post 1st vaccination.
 

 
To evaluate the humoral immune response to the pertussis component of the dTpa vaccine when given alone and co-administered with 2 dose levels (60 and 120 µg) of RSVPreF3 at Screening and Day 31 post 1st dose vaccination by formulation.
 
	
 
Antibody concentrations against pertussis toxoid (anti-PT), filamentous hemagglutinin (anti-FHA), and pertactin (anti-PRN) concentrations at Screening and Day 31.
 

 
To evaluate the humoral immune response to the diphtheria (D) component of dTpa vaccine when given alone and co-administered with 2 dose levels (60 and 120 µg) of RSVPreF3 at Screening and Day 31 post 1st dose vaccination by formulation.
 
	
 
Anti-D concentrations at Screening and Day 31.
 

 
To evaluate the humoral immune response to the tetanus (T) component of dTpa vaccine when given alone and co-administered with 2 dose levels (60 and 120 µg) of RSVPreF3 at Screening and Day 31 post 1st dose vaccination by formulation.
 
	
 
Anti-T concentrations at Screening and Day 31.
 

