**CONFIDENTIAL**

209141 (RSV MAT-011)  
Protocol Amendment 6 Final

\*All subject groups will be given RSV 120mcg and subjects will be followed in an unblinded open label manner

\*\* Hematological and biochemical laboratory testing at Visit 4 (D -7 up to and including 2nd dose vaccination) at the investigator's discretion

\*\*\* There will be no follow-up between C1 and V4. New medical history and relevant new safety events during this period will be recorded at visit 4 for subjects who agree to the study extension and sign the informed consent addendum.

**CONFIDENTIAL**209141 (RSV MAT-011)  
Protocol Amendment 6 Final

The study will be conducted with 2 formulations of dTpa, dTpa\_300 (in the US) and dTpa\_500 (ex-US).

Approximately 500 eligible subjects (250 in the US and 250 ex-US) will be enrolled. Of these, approximately 250 subjects will be randomized to 5 US study groups in a 1:1:1:1:1 ratio using SBIR, and the remaining approximately 250 will be randomized to 5 ex-US study groups in a 1:1:1:1:1 ratio using SBIR. The randomization algorithm will use a minimization procedure by treating study formulation (US and ex-US) as a stratification factor, and age at the time of vaccination (18-32 or 33-45 years of age) and center as minimization factors.

Protocol waivers or exemptions are not allowed unless necessary for the management of immediate safety concerns. Therefore, adherence to the study design requirements, including those specified in the schedule of activities (Section 2), are essential and required for study conduct.

- Type of study: self-contained
- Experimental design:
  - Primary Vaccination: multi-centric study, multi-country Phase II, observer-blind, randomized, with 5 parallel groups in each formulation (US, ex-US).
- Study Extension: multi-centric study, multi-country Phase II, open unblinded, with all 5 parallel groups in each formulation (US, ex-US) receiving the experimental RSV maternal (120 $\mu$ g) vaccine.
- Duration of the study: The primary study will be approximately 6 months for each enrolled subject and from 18 up to 24 months for subjects that agree to participate in the study extension.
  - Primary Vaccination
    - Epoch 001: Screening
    - Epoch 002: Primary vaccination starting at Visit 1 (Day 1) and ending just before the Visit 3 (Day 31)
    - Epoch 003: Follow-up after Visit 3 (Day 31) to Phone Contact 1 on (Day 181)

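### SAP Table 4 leaves Visit 4 out of the elimination code for vaccine-related infection, so a reported RSV infection after Day 31 cannot be removed from the per-protocol persistence result under its own code

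*SAP*

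**What the plan says.** The visit-specific elimination rules are in SAP Amendment 4, section 4.2.2.1, Table 4.

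- Code 2060.Vx+ covers "Concomitant infection related to the vaccine which may influence immune response". Its visit cell reads "Visit 2/Day 8 Visit 3/Day 31 Visit 6".
- Code 2070.Vx+ covers "Concomitant infection not related to the vaccine but may influence immune response" and lists Visits 2, 3, 4 and 6.
- Code 2050.Vx+ covers "Intercurrent medical conditions which are exclusionary as per protocol" and lists Visits 3, 4 and 6.
- The footnotes say that Vx+ removes data from the named visit onward, and that these codes are assigned after CRDL review of individual listings.

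SAP section 4.1.2 defines the per-protocol set by time point and names Visit 4. SAP section 5.2.1 makes that set the main one for immunogenicity. Persistence is a secondary objective in Protocol section 4, Table 5: "RSV A neutralizing antibody titers at Screening, Day 8, Day 31, and a single timepoint between 12 to 18 months post" the first vaccination, with RSV IgG on the same schedule. The late sample is Visit 4.

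The notes to Figure 1 in Protocol section 5.2 say "There will be no follow-up between C1 and V4", C1 being the Day 181 phone contact. Protocol section 8.3.2 has significant conditions from that gap reviewed before the second dose and entered as medical history. The Schedule of Activities (Table 3) records intercurrent conditions at Phone Contact 1 and at Visit 4.

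Protocol section 7.6 allows a subject to be left out of the per-protocol immunogenicity set if "they incur a condition that has the capability of altering their immune response". The wording is permissive, and the example given is varicella.

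**The concern.** For the RSV assays, the natural reading of code 2060 is infection with RSV itself. That is the infection most directly able to raise the antibody being measured. Yet at the persistence visit the table provides for removing an unrelated infection and makes no such provision, in the dedicated row, for the related one.

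Two things follow for a woman with a reported RSV infection after Day 31. Her Visit 4 titre can be counted as durability of the first dose. She can then be dropped under code 2060 from Visit 6, so the GMTs before and after the second dose rest on different women because of her infection. The complementary Exposed Set analysis does not help, since it keeps her as well.

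**Working it through.** **Row check of Table 4 (SAP Amendment 4), visit-specific codes**

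| Code | Visits listed | Visit 4? |
|---|---|---|
| 2040 medication | 2, 3, 4, 6 | yes |
| 2040 device | 2, 3, 6 | no |
| 2050 intercurrent condition | 3, 4, 6 | yes |
| 2060 vaccine-related infection | 2, 3, 6 | no |
| 2070 unrelated infection | 2, 3, 4, 6 | yes |
| 2090, 2100, 2120, 2130 | 2, 3, 4, 6 | yes |

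Only the device row shares the omission. SAP section 8, on changes from planned analyses, does not mention it.

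**What the Vx+ rule does.** An infection coded at Visit 2 or Visit 3 carries forward and removes the Visit 4 result. One arising after Day 31 can first be coded under 2060 at Visit 6.

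**Length of the window.** Protocol Table 4 puts Visit 5 at 365 to 548 days after Visit 1, with Visit 4 up to 7 days before Visit 5.

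- Day 31 to Visit 5: 365 − 31 = 334 days, up to 548 − 31 = 517 days.
- Of that, the part with no planned contact, Day 181 to Visit 5: 365 − 181 = 184 days, up to 548 − 181 = 367 days.

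**Possible size.** The plan states no figure for this, so there is nothing to reproduce. Suppose a share p of a group has a retained infection that leaves the Visit 4 titre f-fold higher. The mean log titre rises by p × log f, so the GMT is multiplied by f^p. Both p and f are assumptions; neither is in the documents.

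| p | f = 2 | f = 4 | f = 8 |
|---|---|---|---|
| 2% | 1.01 | 1.03 | 1.04 |
| 5% | 1.04 | 1.07 | 1.11 |
| 10% | 1.07 | 1.15 | 1.23 |
| 20% | 1.15 | 1.32 | 1.52 |

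The omitted cell affects only *reported* infections, so p is the reported share. With no RSV testing planned, p depends on diagnoses made outside the study, and nothing in the documents supports the lower rows of the table.

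**Scale.** Protocol section 10.1.2 takes an SD of 0.4 on log10, observed 30 days after vaccination. The stated 90% half-width of 0.133 for 50 per group reproduces: t(0.95, 98 df) × 0.4 × √(2/50) = 0.1328. If the same SD held at Visit 4, the within-group 95% CI would be:

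- n = 50: t × 0.4/√50 = 0.114 on log10, a factor of about 1.30 either way.
- n = 100: t × 0.4/√100 = 0.079, a factor of about 1.20.

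Most of the assumed multipliers lie inside those widths.

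**Between groups.** With equal p and f in both groups, the GMT ratio does not change. With p = 5% against 10% and f = 4, it is multiplied by 4^(0.05 − 0.10) = 0.93.

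**The case against.** The best answer is code 2050. It applies at Visit 4, and through Protocol section 7.6 it reaches any condition able to alter the immune response, which a reported RSV infection would be. A reader might infer from the code 2060 row that such a woman cannot be removed from Visit 4 at all. That goes too far: she cannot be removed *under the dedicated code*. Code 2050 does not close the gap, however. Section 7.6 is permissive and does not name RSV, and someone applying Table 4 could fairly take the explicit 2060 visit list as governing RSV. The decision would then rest on case-by-case review in an open-label extension.

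A reader might also infer that the whole interval is unmonitored. It is not. Day 181 has a phone contact, and conditions from the later gap are collected retrospectively at Visit 4.

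The superseded SAP Amendment 3 table, bound with the current one, listed a Visit 4 for code 2060 and none for code 2050. That fits either a deliberate shift or an editing slip, and nothing here depends on which.

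Three further limits stand. RSV is assayed at Visit 4 in all groups, so the dTpa-placebo groups show the background change from natural exposure. Unrecognised infections stay in the set whatever Table 4 says. The endpoint is secondary, and SAP section 6 calls the comparative analyses descriptive.

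**Conclusion.** The omission is real, unexplained and inconsistent with code 2070. As written, a reported RSV infection between Day 31 and Visit 4 has no dedicated route out of the per-protocol persistence result, though it has one out of the Visit 6 result. This assumes that infection related to the vaccine means RSV for the RSV assays, a term the SAP does not define further.

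For any retained infection that raises titres, the within-group Visit 4 GMT or GMC moves upward. A reader might go further and conclude that reported persistence is materially inflated. The documents do not support that: they give no infection rate or fold-rise, the multipliers above are illustrations only, and code 2050 may remove some of the women concerned. Between-group ratios change only if infection, or its effect on titre, differs between groups. The Day 31 primary immunogenicity analysis is untouched, because code 2060 does apply at Visits 2 and 3. The table should be corrected, but no main conclusion of the trial depends on it.

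**What to change.** Add Visit 4 to the code 2060.Vx+ row of SAP Table 4, so that it matches code 2070. Present Visit 4 GMT/GMC with and without women who reported an RSV infection, next to the dTpa-placebo groups as the background change from natural exposure.

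Do not try to catch unreported infections by excluding women whose Visit 4 titre exceeds their own Day 31 value. That selects on the outcome: it lowers estimated persistence even when nobody was infected, and it misses infected women whose titre stays below Day 31. In the dTpa-placebo groups, which had no RSV antigen at the first dose, it would also drop women through assay variation alone.

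The cost is one table cell and one supplementary table, using information already collected at Visit 4. The downside is that a few women leave the Visit 4 per-protocol set, and unreported infections remain in it.
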